5.8 Prohibited therapies and medication

Use of the following concomitant therapies is prohibited during study treatment as described below:

- Investigational therapy (other than protocol-mandated study treatment) is prohibited during study treatment.
- Any concomitant therapy intended for the treatment of cancer (including, but not limited to, chemotherapy, hormonal therapy, immunotherapy, biologic therapy, or radiotherapy) is prohibited until after the end of study visit.
- Hormone replacement therapy, topical estrogens (including any intra-vaginal preparations), megestrol acetate, oral contraception, hormone-eluting intrauterine devices, Gonadotropin-releasing hormone (GnRH) agonists and selective ER modulators (e.g., raloxifene) are prohibited until after the end of study visit.

- Treatment with strong CYP3A4 inhibitors or inducers within 14 days or 5 drug elimination half-lives (whichever is longer) prior to randomization. *Note: this includes consumption of grapefruit, grapefruit juice, grapefruit supplements, or Seville oranges (potent CYP3A inhibitors) within 3 days prior to randomization.*
- Potent inhibitors of CYP2D6 (e.g. paroxetine, fluoxetine, quinidine, cinacalcet or bupropion).

The investigator should consult the prescribing information in giredestrant's (GDC-9545) IB and tamoxifen's SmPC for information on prohibited therapies and recommended dose adjustments for concomitant medications. Giredestrant DDI study (GP44001) suggests that giredestrant is a moderately sensitive CYP3A substrate. It is advised that investigators consider alternatives to the concomitant use of moderate CYP3A inducers with giredestrant or giredestrant combination treatment. If this is not possible or there are no suitable alternatives, co-administration with moderate CYP3A inducers should be generally limited to short term use (approximately 30 days). Concomitant medications that inhibit CYP2D6 may lead to reduced concentrations of the active tamoxifen metabolite endoxifen. Therefore, potent inhibitors of CYP2D6 (e.g. paroxetine, fluoxetine, quinidine, cinacalcet or bupropion) should whenever possible be avoided during tamoxifen treatment. Patients with rare hereditary problems of galactose intolerance, the Lapp lactase deficiency or glucose-galactose malabsorption should not take tamoxifen.

In addition, the investigator should contact the study Medical Monitor if questions arise regarding medications not listed above. Enrolled patients who subsequently require the use of any prohibited therapies must be discontinued from study treatment.

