5.7 General concomitant medication and additional assistance guidelines

Concomitant treatment and prior medication are defined as non-investigational medicinal product (non-IMP). Concomitant treatment includes any prescription drugs, over-the-counter drugs, vaccines, herbal or homeopathic remedies, nutritional supplements) used by a patient in addition to protocol-mandated treatment from 7 days prior to initiation of study drug to treatment discontinuation or end of study visit.

Information on concomitant medication will include start date, end date, brand or generic name, route of administration, dose, and treatment indication. The following **concomitant treatments** are permitted during the study:

- Symptomatic anti-emetics and anti-diarrheal therapy may be administered at the investigator's discretion.
- Bone-sparing agents (e.g., bisphosphonates, denosumab for the treatment of osteoporosis/osteopenia) are allowed in the study provided patients are on stable doses for at least 4 weeks prior to randomization.
- Patients can be treated per standard of care except for use of any prohibited therapies.

All concomitant medication and/or therapies should be documented in the patient's eCRF.

Cautionary therapies may include:

- ***Medications Associated with Bradycardia***

Investigators should use medical judgment and exercise caution when considering initiation of concomitant medication known to cause decreases in heart rate including, but not limited to, β -blockers and calcium channel antagonists. An alternative therapy should be used when possible.

Patients on a stable dose of a β -blocker or calcium channel antagonist for preexisting baseline conditions (e.g., hypertension) should be monitored closely in case dose modification is warranted.

- **Herbal Therapies**

Herbal therapies not intended for the treatment of cancer may be used during the study at the discretion of the investigator and must be reported as concomitant therapy in the eCRF.

Any medications deemed necessary to ensure patient safety and well-being may be administered at the discretion of the investigator with the exception of prohibited therapies contained in **Section 5.8**.

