5.8.1 Interaction with other drugs

Interaction of giredestrant (GDC-9545) with other medicinal products and other forms of interaction

Giredestrant is a moderately sensitive CYP3A substrate. Co-administration giredestrant with the strong CYP3A inhibitors and inducers should be avoided. Refer to the giredestrant's (GDC-9545) IB for a complete summary of safety information and DDIs.

Interaction of tamoxifen with other medicinal products and other forms of interaction

When tamoxifen is used in combination with coumarin-type anticoagulants, a significant increase in anticoagulant effect may occur. Where such co-administration is initiated, careful monitoring of the patient is recommended.

As tamoxifen is metabolized by cytochrome P450 3A4, care is required when co-administering with drugs, such as rifampicin, known to induce this enzyme as tamoxifen levels may be reduced. The clinical relevance of this reduction is unknown. Therefore, is recommended to avoid the coadministration of tamoxifen and CYP3A inhibitors/inducers.

Pharmacokinetic interaction with CYP2D6 inhibitors, showing a 65-75% reduction in plasma levels of one of the more active forms of the drug, i.e., endoxifen, has been reported in the literature. Reduced efficacy of tamoxifen has been reported with concomitant usage of some SSRI antidepressants (e.g. paroxetine) in some studies.

As a reduced effect of tamoxifen cannot be excluded, co-administration with potent CYP2D6 inhibitors (e.g. paroxetine, fluoxetine, quinidine, cinacalcet or bupropion) should whenever possible be avoided.

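### Potent CYP2D6 inhibitors are banned in Protocol 5.8 but only discouraged later in 5.8 and in 5.8.1, and no washout covers a patient who stops one just before Day 1

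*Protocol*

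**What the plan says.** Protocol 5.8 opens with "Use of the following concomitant therapies is prohibited during study treatment as described below". One item on the list that follows is "Potent inhibitors of CYP2D6 (e.g. paroxetine, fluoxetine, quinidine, cinacalcet or bupropion", with no limit to one arm and no time window. Two other rules give the list force. Under 5.7, medication needed for a patient's safety and well-being "may be administered at the discretion of the investigator with the exception of prohibited therapies contained in" Section 5.8. The close of 5.8 says "Enrolled patients who subsequently require the use of any prohibited therapies must be discontinued from study treatment".

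The explanatory paragraph below the list then says that the same five example drugs "should whenever possible be avoided during tamoxifen treatment". Section 5.8.1 says that "co-administration with potent CYP2D6 inhibitors (e.g. paroxetine, fluoxetine, quinidine, cinacalcet or bupropion) should whenever possible be avoided". It gives the reason: an interaction "showing a 65-75% reduction in plasma levels of one of the more active forms of the drug", endoxifen. It adds: "Reduced efficacy of tamoxifen has been reported with concomitant usage of some SSRI antidepressants (e.g. paroxetine) in some studies". It also accepts that a weaker tamoxifen effect cannot be ruled out. For giredestrant, 5.8 and 5.8.1 describe a CYP3A interaction and name none through CYP2D6.

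On eligibility, exclusion criterion 12 (Protocol 4.3, synopsis, SAP 1.3.3) bars strong CYP3A4 inhibitors or inducers taken within the longer of 14 days and five half-lives before randomisation. No inclusion or exclusion criterion names CYP2D6. Criterion 19 excludes a patient who, in the investigator's opinion, cannot or will not follow the protocol. Under 6.1.2 the medical monitor verifies eligibility before inclusion.

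**The concern.** There are two linked gaps. First, the protocol gives two instructions for the same drugs, and they lead to different actions. Under the ban, a tamoxifen patient who comes to need paroxetine must stop study treatment. Under the weaker sentences, an investigator who judges avoidance impossible could keep her on both drugs.

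Second, the ban applies during study treatment and says nothing about the days before it. A patient who stops a potent inhibitor the day before Day 1 complies with 5.8 and meets every criterion in 4.3. The sponsor set a washout for strong CYP3A4 agents but not for this class.

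The interaction is described for the comparator only. If inhibition persists into the 15-day course, tamoxifen may suppress Ki67 less than it otherwise would, and the comparison shifts toward giredestrant. The trial's purpose is to show giredestrant superior to tamoxifen, so a one-directional influence deserves closing even if it is small.

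**Working it through.** **Text check.** The plan gives no figure on this point, so the first step is to follow each type of patient through the rules.

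| Patient | Rule that applies | Result |
|---|---|---|
| Takes an inhibitor at screening and cannot stop | Ban in 5.8; criterion 19 | Can be excluded, by judgement and not by name |
| Starts needing one after enrolment, ban followed | 5.7 and the close of 5.8 | Study treatment stops |
| Starts needing one after enrolment on tamoxifen, weaker text followed | Later text of 5.8; 5.8.1 | May continue both |
| Stops one shortly before Day 1 | None | Enters with no washout |

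The third and fourth rows are the problem. The medication history does not reliably expose the fourth patient, because the look-back differs by place. It is 7 days before study drug in Protocol 3.3.2 and 5.7, 14 days in Appendix 1 note 10, and 28 days before enrolment in Appendix 1 note 2.

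**Size, as illustration only.** The documents give neither the frequency of use nor the loss of Ki67 effect at 15 days. Inputs from the plan (Protocol 8.2) are 46 per arm, 10% dropout, assumed means of 70% and 50%, and SD 29%. Evaluable per arm: 46 × 0.9 = 41.4, taken as 41. Assumed: 1, 2 or 4 affected tamoxifen patients, each losing a quarter or half of the 50-point effect.

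Shift in the tamoxifen mean = 50 × (users / 41) × loss:

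- 1 user: 50 × 1/41 × 0.25 = 0.30; with loss 0.5, 0.61. Against the 20-point planned gap this is 1.5% to 3.0%.
- 2 users: 0.61 to 1.22 points (3.0% to 6.1%).
- 4 users: 1.22 to 2.44 points (6.1% to 12.2%).

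For the planned test, trials were simulated with the two drugs truly equal, 200,000 per case, using a two-sided 0.05 Wilcoxon rank-sum test (normal approximation) on absolute change = baseline × percent reduction. Percent reduction was normal (mean 50, SD 29) capped at 100. Affected patients had mean 37.5 or 25. Baseline Ki67 was assumed lognormal, limited to 10–90%, with median 20 (log SD 0.4) or 25 (log SD 0.5) before truncation. Ranges cover both losses and both baselines.

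| Affected tamoxifen patients of 41 | Significant in favour of giredestrant | Any two-sided rejection |
|---|---|---|
| 0 | 2.5% | nominal 5% |
| 1 | 2.7–3.0% | 5.0% |
| 2 | 2.9–3.5% | 4.9–5.2% |
| 4 | 3.5–4.9% | 5.1–6.0% |

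These cases treat the loss as lasting the whole course. If inhibition fades after the drug is stopped, a recent stopper would lose less.

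**The case against.** The strongest reply is that the ban is the operative rule. The list in 5.8 is unqualified, 5.7 removes investigator discretion over it, and the weaker sentences sit in explanatory interaction text. A patient still taking paroxetine on Day 1 would then be a protocol breach, not something the plan permits. Criterion 19 reaches the patient who cannot comply as well as the one who will not, and the medical monitor reviews eligibility before inclusion. Other banned therapies, such as topical estrogens and GnRH agonists, also lack a dedicated exclusion in 4.3. The size rests wholly on assumed user counts and losses.

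Much of this stands. It lowers the priority and limits the entry gap to the recent stopper. It does not remove the conflict, because the weaker sentences are still addressed to investigators and would let a patient continue where the ban would stop her. Nor do criterion 19 or the monitor's check reach a patient who stops the day before: she complies, and there is no criterion against which to reject her. The comparison with other banned therapies shows that a washout is not automatic. It does not answer the protocol's own statement that this class may weaken the comparator.

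**Conclusion.** The point holds as a minor one: two stated rules conflict, and one route into the trial has no washout. Any residual effect would favour giredestrant, given that the documents name no CYP2D6 interaction for that drug. The size cannot be derived and is probably small. With one or two affected patients, the chance of a false finding for giredestrant is 2.7–3.5% against 2.5%, under the assumptions shown.

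Three stronger readings are not supported:

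- A reader might infer that the plan knowingly admits women still taking an inhibitor. The ban applies from the start of treatment, so that would be a deviation.
- A reader might infer that stopping such patients biases the primary analysis, since under 14 days of treatment removes them from the mITT set. The ban covers both arms, so this loss has no stated direction. The discontinuation rule is also worded for a need that arises after enrolment.
- A reader might infer a large error. A simple mean-comparison calculation gives about 13% in favour of giredestrant, but only if 15% of the tamoxifen arm (0.15 × 41, about 6 patients) each lost 70% of the effect. That is a shift of 50 × 0.15 × 0.70 = 5.25 points, and nothing in the documents supports those inputs.

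**What to change.** 1. In 5.8 and 5.8.1, replace the two conditional sentences with a reference to the ban in 5.8.
2. Extend criterion 12 in Protocol 4.3, the synopsis and SAP 1.3.3 to potent CYP2D6 inhibitors taken within the longer of 14 days and five elimination half-lives before randomisation. The window is borrowed from the CYP3A4 rule, because the documents give no figure specific to CYP2D6. Apply it as an exclusion, so that no patient is asked to give up a needed drug in order to enter. Set one prior-medication look-back of at least 28 days, and ask about earlier use where five half-lives is longer.
3. If enrolment is complete, list potent CYP2D6 inhibitor use by arm. Repeat the primary Wilcoxon test excluding, from both arms, patients with recorded use inside that pre-randomisation window. Selecting on use before randomisation keeps the exclusion independent of post-randomisation events. List on-treatment use separately as protocol deviations. The listing can show only what sites recorded, which may be 7 or 14 days where the shorter look-back was followed.

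The cost is low: one extended criterion in three places and a few sentences, or one listing and one repeat test on medication data that SAP 4.5.4 already has coded. The downside is that a few otherwise eligible patients are excluded.

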- Hepatic: total serum bilirubin $\leq 1.5 \times$ institutional upper limit of normal (ULN) (patients with known Gilbert's syndrome: $\leq 3 \times$ ULN); alkaline phosphatase (ALP) ≤ 2.5 times ULN; aspartate transaminase (AST) and serum alanine transaminase (ALT) $\leq 3 \times$ times ULN.

- Coagulation: The international normalized ratio (INR) < 1.5' ULN and partial thromboplastin time (PTT or aPTT) < 1.5' ULN (except for patients receiving anticoagulation therapy). For patients receiving warfarin, a stable INR between 2 and 3 is required. For patients receiving heparin, PTT (or aPTT) between 1.5 and 2.5' ULN (or patient value before starting heparin treatment) is required. If anticoagulation therapy is required for a prosthetic heart valve, stable INR between 2.5 and 3.5 is permitted.
 - Renal: creatinine clearance ≥ 60 mL/min for patients with creatinine levels above institutional normal.
8. Negative serum pregnancy test result within 14 days prior to initiation of study treatment and a negative urine pregnancy test within 24 hours prior to study treatment initiation.

Note: Premenopausal women age ≥ 18 years with premenopausal status defined as: estradiol (E2) in the premenopausal range (according to institution parameters) or patient has been menstruating regularly during the 6 months prior to randomization and has not used any form of hormonal contraception or any other hormonal treatments during this time.

Women must remain abstinent and truly abstains from sexual activity (refrains from heterosexual intercourse) or use of locally recognized adequate methods of contraception (described as that with a failure rate <1%) during the length of the study, and to continue its use for 10 days after the last dose of study treatment (for patients taking giredestrant) or 9 months following cessation of therapy (for patients in the tamoxifen arm). They must, as well, agree to refrain from donating eggs during the same period of time.

Examples of non-hormonal contraceptive method with a failure rate of <1% per year (e.g. bilateral tubal ligation, male sterilization and copper intrauterine devices). The reliability of sexual abstinence should be evaluated in relation to the duration of the clinical trial and the preferred and usual lifestyle of the individual. Periodic abstinence (e.g., calendar, ovulation, symptothermal, or postovulation methods) and withdrawal are not adequate methods of contraception.

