 - History of documented congestive heart failure (New York Heart Association Class II-IV) or cardiomyopathy.
 - QT interval corrected through use of Fridericia's formula (QTcF) >470 ms by at least three ECGs >30 minutes apart.
 - History of long or short QT syndrome, Brugada syndrome or known history of corrected QT interval prolongation, or torsades de pointes.

- History or presence of an abnormal ECG that is clinically significant in the investigator's opinion.
 - History of ventricular dysrhythmias or risk factors for ventricular dysrhythmias such as structural heart disease (e.g., severe left ventricular systolic dysfunction, left ventricular hypertrophic cardiomyopathy, infiltrative cardiomyopathy, moderate-to-severe valve disease), coronary heart disease (symptomatic or with ischemia demonstrated by diagnostic testing), clinically significant electrolyte abnormalities (e.g., hypokalemia, hypomagnesemia, hypocalcemia), or family history of long QT syndrome.
11. Any serious medical condition or abnormality in clinical laboratory tests that, in the investigator's judgment, precludes the patient's safe participation in and completion of the study.
 12. Treatment with strong CYP3A4 inhibitors or inducers within 14 days or 5 drug elimination half-lives (whichever is longer) prior to randomization.
 13. Active inflammatory bowel disease or chronic diarrhea, short bowel syndrome, or major upper gastrointestinal surgery including gastric resection.
 14. Participants who have a known allergy or hypersensitivity to any of the study drugs or any of their excipients.
 15. Participants who are pregnant or breastfeeding or intending to become pregnant during the study or within 10 days after the final dose of giredestrant (GDC-9545), or within 9 months after the final dose of tamoxifen.

Note: Women of childbearing potential must have a negative serum pregnancy test result within 14 days prior to initiation of study treatment and a negative urine pregnancy test within 24 hours prior to study treatment initiation.

16. Patients with renal dysfunction who require dialysis.
17. Participants who have had a serious infection requiring oral or IV antibiotics within 14 days prior to screening or other clinically significant infection (e.g., COVID-19) within 14 days prior to screening.

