6.1.2 Patient allocation

The following steps must be taken before registering patients to this study:

1. Completion of patient eligibility checklist by the investigational site, once checked all selection criteria. For patients with locally determined basal Ki67 between 10% and 19%, after receiving central Ki67 score result.

Note for Ki67 selection criteria: Ki67 will be analyzed locally at the time of inclusion. For patients with basal Ki67 $\geq 20\%$ according to local analysis, Ki67 $\geq 10\%$ will be centrally confirmed retrospectively after inclusion. For patients with basal Ki67 levels between 10% and 19% according to local analysis, Ki67 $\geq 10\%$ will need to be centrally confirmed before inclusion.

2. Registration of patient in the Sponsor's study database.
3. Randomization using Sponsor's study database.

Confirmation of patient allocation using Sponsor study database:

Each patient will be identified with a unique patient number (UPN) for this study obtained from eCRF. All data will be recorded with this identification number on the appropriate eCRFs.

Confirmation of patient's eligibility for study participation will be recorded on the eCRF by the investigational site and verified by the study medical monitor prior to inclusion (all screening data needs to be completed 48h prior to randomization to allow enough time for medical monitor review). The investigator is responsible for safeguarding patient information (i.e., age, name, address, telephone number, social security number, and study identification number), ensuring access to this information by Health Authorities if necessary. These records will remain confidential for the period of time stipulated by current legislation.

Randomization

Premenopausal women with ER[+]/HER2[-] and Ki6 $\geq 10\%$ early breast cancer will be randomized in a 1:1 ratio to giredestrant (GDC-9545) or tamoxifen arms.

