9. **AE reporting:** After informed consent has been obtained but prior to initiation of study drug, only serious adverse events caused by a protocol-mandated intervention should be reported with grading according to the NCI–CTCAE v.5.0 criteria. After initiation of study drug, all adverse events will be reported until 28 days (EoS) after the final dose of study treatment. After this period, the Sponsor should be notified if the investigator becomes aware of any serious adverse event that is believed to be related to prior study drug treatment.
10. **Concomitant medication reporting:** Medication (e.g., prescription drugs, over-the-counter drugs, vaccines, herbal or homeopathic remedies, nutritional supplements) used by a patient in addition to protocol-mandated treatment from 14 days prior to initiation of study drug until end of study visit.
11. **12-lead ECG:** Patients should be resting in a supine position for at least 10 minutes prior to ECG recording. All ECGs will be obtained prior to other procedures scheduled at that same time (e.g., vital sign measurements, blood draws). All patients must have a standard 12-lead ECG in screening period, maximum 48h before start of treatment dose, in the EoT visit and in the EoS visit.
12. **Laboratory assessments:** These values should include: hematological test (hemoglobin, hematocrit, red blood cell count, platelet count, WBC and differential count [ANC, lymphocytes, monocytes, eosinophils and basophils, and other cells]); coagulation (INR, PTT (or aPTT)); chemistry panel (serum or plasma): sodium, potassium, chloride, glucose, BUN or urea, creatinine, total protein, albumin, phosphate, calcium, total bilirubin (if total bilirubin is 2xULN, also direct bilirubin), AST, ALT, ALP, urate and LDH; fasting lipid panel: cholesterol, LDL cholesterol, HDL cholesterol, and triglycerides (after ≥ 8 hours of fasting); urinalysis, including dipstick (pH, specific gravity, glucose, protein, ketones, and blood) and microscopic examination (sediment, RBCs, WBCs, casts, crystals, epithelial cells, and bacteria), FSH and estradiol. Baseline (Day 1, prior to initiation of study treatment) laboratory assessments are not required if the screening assessments were performed at within 14 days prior to initiation of study treatment.

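### Section 5.8 names women who should not be given tamoxifen, but no eligibility criterion identifies them before 1:1 randomisation to it

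*Protocol*

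**What the plan says.** **Hereditary conditions.** Protocol section 5.8, which otherwise lists prohibited therapies, ends a paragraph with a statement about patients: "Patients with rare hereditary problems of galactose intolerance, the Lapp lactase deficiency or glucose-galactose malabsorption should not take tamoxifen". It makes no matching statement about giredestrant. Under section 6.1.2 eligible women are "randomized in a 1:1 ratio to giredestrant (GDC-9545) or tamoxifen arms".

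The nearest exclusions in section 4.3 are:

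- Criterion 11: "Any serious medical condition or abnormality in clinical laboratory tests that, in the investigator's judgment, precludes the patient's safe participation".
- Criterion 13: "Active inflammatory bowel disease or chronic diarrhea, short bowel syndrome, or major upper gastrointestinal surgery including gastric resection".
- Criterion 14: "Participants who have a known allergy or hypersensitivity to any of the study drugs or any of their excipients".

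Inclusion criterion 10 asks that the patient can swallow, keep down and absorb oral medicine. The opening of section 4 asks investigators to weigh all relevant conditions when judging suitability. SAP sections 1.3.2 and 1.3.3 repeat the same criteria.

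**Anticoagulants.** Inclusion criterion 7 in section 4.2 admits women on warfarin: "For patients receiving warfarin, a stable INR between 2 and 3 is required". Section 5.8.1 warns: "When tamoxifen is used in combination with coumarin-type anticoagulants, a significant increase in anticoagulant effect may occur". It then recommends careful monitoring when the two drugs are started together, without naming a test, a day or a frequency. In Appendix 1 the laboratory panel, which includes INR, is marked at screening, Day 1, end of treatment (EoT) and end of study (EoS). The Days 2-15 column is empty. Footnote 12 waives the Day 1 panel: "laboratory assessments are not required if the screening assessments were performed at within 14 days prior to initiation of study treatment".

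**The concern.** Allocation is not known at screening, so a restriction that applies to only one of the two drugs has to be checked in every woman before she is randomised. Section 6.1.2 bases the pre-randomisation check on a checklist of the selection criteria, which the medical monitor verifies. A restriction that stands outside those criteria has no fixed place in that check.

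Two things are at stake. The first is safety: a woman whom the protocol's own text says should not have the comparator could be assigned to it. The second is the comparison. If the restriction is noticed after allocation and she does not take tamoxifen, she is lost from the primary analysis set, and this can happen in one arm only. The trial is open-label, so the site will know which arm she is in.

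The anticoagulant text raises a lesser question of the same kind. Section 5.8.1 states a precaution for tamoxifen, and the visit schedule contains nothing that carries it out during treatment.

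**Working it through.** The plan gives no figure on this point, so there is none to reproduce. The check sets the passages side by side and adds a day count.

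**Step 1: does any criterion cover the three conditions?**

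| Provision | What it covers | Names the conditions? |
|---|---|---|
| Inclusion 10 | Swallowing, retaining and absorbing oral medicine | No |
| Exclusion 11 | Serious conditions, by investigator judgment | No |
| Exclusion 13 | Listed bowel disease, chronic diarrhoea, surgery | No |
| Exclusion 14 | Allergy or hypersensitivity to a drug or excipient | No |
| Section 4, opening | General suitability | No |

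The remaining criteria among the 10 inclusions and 19 exclusions deal with other matters. The synopsis and the SAP copy add nothing.

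**Step 2: what happens to such a woman after randomisation?** The mITT set (Protocol 8.3, SAP 3) requires central Ki67 of at least 10%, at least 14 days of treatment, and central Ki67 at baseline and after treatment.

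- Allocated to tamoxifen and treated: she stays in the set, contrary to section 5.8.
- Allocated to tamoxifen and not treated, or stopped before 14 days: she leaves the set.
- Allocated to giredestrant: section 5.8 gives no reason to stop, so she stays if otherwise evaluable.

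The exclusion in the second case depends on the arm.

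**Step 3: size.** Let k be the number of randomised women with one of the conditions. The documents call the conditions rare and give no prevalence, so k is unknown. With 1:1 allocation the expected number in the tamoxifen arm is k × 1/2. Each woman lost there is 1/46 = 2.2% of the 46 planned for that arm. Nothing in the sample size calculation (Protocol 8.2, SAP 1.6) depends on k.

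**Step 4: scheduled INR for a warfarin user.** First dose is on Day 1. The EoT visit falls on Day 15 or 16, or on Day 17 if treatment is extended to 16 days.

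- First dose to next scheduled INR: 15 − 1 = 14 days, 16 − 1 = 15 days, or 17 − 1 = 16 days.
- If the Day 1 panel is waived because screening laboratory tests were done up to 14 days before first dose, the longest interval between scheduled INRs is 14 + 14 = 28, 14 + 15 = 29, or 14 + 16 = 30 days. The first 14 of those days precede any tamoxifen.
- Scheduled INRs after first dose and before EoT, which is also the biopsy or surgery visit: none.

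**The case against.** **On the hereditary conditions.** The protocol does have safeguards. Investigators must weigh all relevant conditions, criterion 11 allows exclusion by judgment, criterion 13 would catch a woman with chronic diarrhoea, and sites are referred to the tamoxifen product information. The medical monitor also verifies eligibility. The site checklist and study manual are not among the documents and may contain the restriction. All this is fair, and it means that many such women would probably be recognised. But these safeguards are either discretionary or tied to the listed criteria, and none expressly covers the three conditions. The wording gap stands.

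It can also be said that the effect on the comparison is close to nil and that the ITT analysis keeps every randomised woman. The first part stands for rare conditions. The second helps only in part. If she has no post-treatment sample, the supportive ITT analysis of the primary endpoint sets her change to zero (Protocol 8.6, SAP 4.4.1.2).

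**On warfarin.** A reader might infer that admitting warfarin users contradicts section 5.8.1. The documents do not support that. Section 5.8.1 recommends monitoring and does not prohibit co-administration. Section 6.5.1 ties laboratory tests to local standards and clinical indications, and section 5.7 allows standard care apart from prohibited therapies, so an unscheduled INR is open to any site. A reader might also infer that INR is not scheduled at all until the invasive procedure. In fact it is scheduled at screening and on Day 1, subject to the waiver, and again at EoS. The gap lies only between first dose and EoT.

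**Conclusion.** The point holds for the hereditary conditions. Section 5.8 sets a restriction on the comparator that the eligibility criteria do not carry, so following the plan as written can place an affected woman on tamoxifen or lose her from the mITT set in that arm only. This rests on the criteria as printed and on the assumption that the unseen checklist mirrors them, as section 6.1.2 suggests.

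The size is small and cannot be put as a number of patients. A reader might be tempted to assume a prevalence of a few per cent, or to infer a loss of power or a material bias. The documents give no basis for a prevalence or for the number of warfarin users, and sample size, power and the primary test are unchanged. The case for acting is that the consequence for an individual woman is avoidable and the correction is cheap.

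The warfarin point is secondary. It is a recommendation with no counterpart in the schedule for the 14 to 16 days between first dose and EoT, and it is not a contradiction.

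**What to change.** Reconcile sections 4.2 and 4.3, the synopsis, the SAP copy and the eligibility checklist with section 5.8. Any woman who, by the protocol's own text, should not take one of the two study drugs should be identified before randomisation, whichever arm she would have entered. Any resulting loss then falls before allocation and is the same for both arms.

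Separately, reconcile inclusion criterion 7, section 5.8.1 and the coagulation entries in Appendix 1, including the footnote 12 waiver, so that a site can see how the recommended monitoring relates to the scheduled tests. What the clinical rule should be in either case is for the medical lead.

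The cost is a wording change to the protocol, the SAP copy and the checklist, and possibly a very few women made ineligible. The sample size and the analysis methods need no change.
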